# 6.3.8. COVID-19 Related Endpoint 4 – Frequency distribution of pneumococcal carriage among participants with and without current/recent COVID-19 infection

Frequency distribution of serotypes for pneumococcal carriage among participants with or without laboratory-confirmed COVID-19 infection, overall and stratified by age, sex, and pneumococcal risk status.

# 6.3.8.1. COVID-19 Related Endpoint 4 - Main Analysis

In this analysis the CAP population will be divided into two groups:

- CAP cases associated with COVID-19 infection
- CAP cases without COVID-19 infection

Distribution of serotype for the pneumococcal carriage between these two groups will be evaluated. Chi-square or Fisher's exact tests, as appropriate will be used to evaluate the difference between the two groups (cases and controls as defined herein).

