- To estimate incidence rates for hospitalised CAP among adults aged ≥60 years with underlying at-risk and high-risk medical conditions, in aggregate and for individual risk conditions within the limitations of the expected under ascertainment of hospital-based screening process and current diagnostic testing.

Additional 2019 Novel Coronavirus Disease 2019 (COVID-19)-related Exploratory Objectives

- To determine if the frequency of pneumococcal infection differs between hospitalised CAP patients with COVID-19 infection compared to those without COVID-19 infection, overall and stratified by age, sex, and pneumococcal risk status.
- Among the subset of hospitalised CAP patients with COVID-19 identified, to determine if the proportion who experience severe clinical outcomes (eg, intensive care unit [ICU] stay, mechanical ventilation, prolonged hospitalisation, and sequelae) differs between those with pneumococcal co-infection compared to those without pneumococcal co-infection, overall and stratified by age, sex, and pneumococcal risk status.
- Using a test-negative design to determine the VE of PCV13 against severe COVID-19 clinical outcomes among COVID-19 positive hospitalised CAP patients, overall and among immunocompetent persons only.
- To assess if pneumococcal carriage differs for those with current or past COVID-19 infection, overall and stratified by age, sex, and pneumococcal risk status.

Additional 2022 Respiratory Syncytial Virus (RSV) Exploratory Objective

• To determine the proportion of persons with RSV infection among adults 60 years of age and older presenting with CAP by testing saliva specimens using the PCR method.

Study design

This study is a low interventional, prospective, multicentre, hospital-based study involving adults 60 years of age and older hospitalised with CAP at participating sites. Hospital surveillance data will be used for incidence rates calculations. Vaccine effectiveness will be calculated using a TND. The approximate study duration will be 4 years.

Population

This study will prospectively enroll adults, aged 60 years and over, who are hospitalised with CAP in one of the study hospitals: Hospital Universitario de Móstoles, Hospital Universitario Fundación de Alcorcón, and Hospital Rey Juan Carlos de Móstoles (as of February 2022, additional sites may be included at a later date).

Variables

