• To assess if pneumococcal carriage differs for those with current or past COVID-19 infection, overall and stratified by age, sex, and pneumococcal risk status.	• Percentage of CAP events with pneumococcal carriage among CAP events associated with a positive COVID-19 test compared to percentage of CAP events with pneumococcal carriage among CAP events associated with a negative COVID-19 test, overall and stratified by age, sex, and pneumococcal risk status.

Additional RSV Exploratory Objective	Additional RSV Exploratory Endpoints
• To determine the proportion of persons with RSV infection among adults 60 years of age and older presenting with CAP by testing saliva specimens using the PCR method).	• Proportion of CAP events where RSV was identified from saliva by PCR divided by all CAP events where the subject had a valid saliva specimen test result.

Note: Saliva samples will be taken only in selected sites.

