 - COVID-19 vaccination, dates and vaccines types.
 - RSV vaccination, dates and vaccine types.
- Hospitalisation data:
 - Dates and time of admission/discharge for qualifying admission.
 - ICU stay (yes/no).
 - Number of days in ICU.
 - Mechanical ventilatory support (invasive and non-invasive), if used and type.
 - Number of days of mechanical ventilator use.
 - Acute respiratory distress syndrome (ARDS) diagnosis during illness.

PFIZER CONFIDENTIAL CT45-GSOP-RF152.0 Low-Interventional Study Protocol Template 05-Dec-2019 Page 36 of 70

- Readmission within 14 days of discharge (If yes, dates of admission/discharge).
- Symptoms of qualifying pneumonia illness mentioned in inclusion criteria.
- Date of illness onset.
- Vital signs (initial respiratory rate, pulse oximetry, blood pressure, heart rate).
- Level of oxygen supplementation during pulse oximetry measurement (FiO2).
- SOC chest radiography results (eg, CXR and computed tomography [CT] scan), including if consistent with pneumonia per standard outlined in Section 11.3.
- SOC microbiology test results including test and specimen type:
 - Blood cultures.
 - Respiratory microbiology testing, including bacterial (eg, PCR and culture), viral testing (eg, RSV, influenza, and COVID-19), and Gram stain results.
 - All standard –of care COVID-19 testing during the qualifying illness will be recorded with result.
 - Pneumococcal testing (eg, *BinaxNOW*[®] or another pneumococcal antigen urine test).
 - Other body fluid/tissue sterile under normal conditions.
- CAP severity/prognosis scale (Confusion Respiratory Rate Blood Pressure [CRB-65] and Pneumonia Severity Index [PSI]) on presentation to hospital if information available from SOC testing to calculate score:
 - CRB-65 score [Contributing data elements: age, blood pressure, presence of confusion, and respiratory rate].
 - PSI score. Contributing data elements are:
 - Altered mental status.
 - Nursing home residency.
 - pH and partial pressure of arterial O2 (PaO2) from atrial blood or arterialised venous blood OR oxygen saturation level (SpO2) measured by pulse oximetry

PFIZER CONFIDENTIAL CT45-GSOP-RF152.0 Low-Interventional Study Protocol Template 05-Dec-2019 Page 37 of 70

and FiO2 during that assessment.

- Blood urea nitrogen.
- Serum sodium concentration.
- Plasma glucose concentration.
- Hematocrit.
- Presence of pleural effusion.
- Relevant medical history:
 - COPD.
 - Asthma.
 - Congestive Heart Failure.
 - Coronary Artery Disease (CAD).

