## 2.1.4. Additional COVID-19 Exploratory Objectives

- To determine if the frequency of pneumococcal infection differs between hospitalised CAP patients with COVID-19 infection compared to those without COVID-19 infection, overall and stratified by age, sex, and pneumococcal risk status.
- Among the subset of hospitalised CAP patients with COVID-19 identified, to determine if
  the proportion who experience severe clinical outcomes (eg, intensive care unit [ICU] stay,
  mechanical ventilation, prolonged hospitalisation, and sequelae) differs between those
  with pneumococcal co-infection compared to those without pneumococcal co-infection,
  overall and stratified by age, sex, and pneumococcal risk status.
- Using a TND to determine the VE of PCV13 against severe COVID-19 clinical outcomes among COVID-19 positive hospitalised CAP patients, overall and among immunocompetent persons only.
- To assess if frequency of pneumococcal carriage differs for those with current or past COVID-19 infection, overall and stratified by age, sex, and pneumococcal risk status.

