- VE calculated as 1 minus the OR comparing the odds of having received PCV13 by cases and controls, multiplied by 100%, overall and among immunocompetent persons only, adjusted for confounders. (Cases=COVID-19-positive CAP subjects with severe clinical outcomes; Controls=COVID-19-positive CAP subjects without severe clinical outcomes. This will be a nested case-control study, and the COVID-19 status will be determined from standard-of-care viral testing. The cases are CAP patients with COVID-19 with severe clinical outcomes, and the controls are the CAP patients with COVID-19 without severe clinical outcomes. Several clinical outcomes will be used in the definition of cases and
  - Patients admitted to the ICU

controls as stated below:

- Patients with PaO2/FiO2 ratio <250 mmHg

- Patients with respiratory rate >30 breaths/min
- Patients died
- Patients received mechanical ventilation
- Patients diagnosed as ARDS
- Any severe clinical outcome mentioned above
- Frequency of pneumococcal carriage among subjects with current/recent COVID-19 infection compared to frequencyof pneumococcal carriage among subjects without current/recent COVID-19 infection, overall and stratified by age, sex, and pneumococcal risk status.
  - In this analysis, the denominator will be the Saliva Carriage Subpopulation with COVID-19 status to be determined from standard-of-care viral testing.

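### The SAP's COVID-19 carriage analysis tests the serotype mix, not the carriage frequency that the objective and endpoint name, and past infection has no planned data source

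*SAP*

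**What the plan says.** **Objective.** The protocol (Summary) states: "To assess if pneumococcal carriage differs for those with current or past COVID-19 infection". SAP 2.1.4 makes the quantity explicit: "To assess if frequency of pneumococcal carriage differs for those with current or past COVID-19 infection".

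**Endpoint.** Protocol section 8 gives: "Percentage of CAP events with pneumococcal carriage among CAP events associated with a positive COVID-19 test", compared with the same percentage in test-negative events, overall and by age, sex and risk status. SAP 3.3.2 gives: "Frequency of pneumococcal carriage among subjects with current/recent COVID-19 infection", compared with subjects without it. The SAP 3.3.2 denominator is the saliva carriage subpopulation, with COVID-19 status taken from standard-of-care viral testing.

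**Analysis.** SAP 6.3.8 describes a frequency distribution of carriage serotypes in participants with and without laboratory-confirmed COVID-19. SAP 6.3.8.1 divides the CAP population into those with and those without COVID-19 infection and continues: "Distribution of serotype for the pneumococcal carriage between these two groups will be evaluated". The test is chi-square or Fisher's exact.

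**Data on COVID-19 infection.** Protocol 10.3 requires that all standard-of-care "COVID-19 testing during the qualifying illness will be recorded with result". Late results may be added at Visit 2 (Protocol 10.4). The medical history list in Protocol 10.3 and the baseline variables in SAP 3.4 include COVID-19 vaccination and current viral tests, but no item for earlier COVID-19 infection.

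**The concern.** Whether carriage is more or less common in COVID-19 patients, and which serotypes the carriers have, are different questions. A programmer working from SAP section 6 would build a serotype table and test it, and the report would carry no planned comparison of the quantity named in the objective. That test can miss a real difference in frequency, and it can turn up a difference when the frequencies are equal.

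The wording for infection status also drifts: 'past' in the objectives, a positive test in the protocol endpoint, 'current/recent' in SAP 3.3.2, laboratory-confirmed in SAP 6.3.8. Only infection at the time of the qualifying illness has a planned data source. A patient with past COVID-19 and a negative current test therefore enters the comparator.

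**Working it through.** The documents give no sample size, power or expected rate for this endpoint, so there is no figure to reproduce. The check sets the texts side by side and then illustrates the consequence.

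**1. Quantity, by section**

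| Place | Quantity |
|---|---|
| SAP 2.1.4 objective | carriage frequency |
| Protocol 8 endpoint | percentage of CAP events with carriage |
| SAP 3.3.2 endpoint | carriage frequency |
| SAP 6.3.8, text | serotype distribution of carriage |
| SAP 6.3.8.1, main analysis | serotype distribution, tested |
| SAP 6.2.2.1 | carriage proportion overall, by risk status and by age; not by COVID-19 status |

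SAP 6.3.5.1, for pneumococcal infection, is written as one would expect here: a proportion with 95% CI among test-positive patients and another among test-negative patients. This suggests that 6.3.8.1 is a drafting slip.

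**2. Population.** SAP 3.3.2 requires a saliva result and a COVID-19 status. SAP 6.3.8.1 starts from the whole CAP population and states neither condition, although the protocol takes saliva only at selected sites. It also refers to cases and controls that the section does not define.

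**3. Same mix, different frequency (assumed inputs).** Take 200 COVID-19-positive and 1,000 negative patients, carriage 10% and 20%, and five serotypes with shares 0.30, 0.25, 0.20, 0.15 and 0.10 in both groups.

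- Carriers by serotype: 6, 5, 4, 3, 2 against 60, 50, 40, 30, 20. Every ratio is 1:10, so chi-square = 0 and p = 1.00.
- Carriage: 20/200 against 200/1,000. The pooled proportion is 220/1,200 = 0.1833. SE = √[0.1833 × 0.8167 × (1/200 + 1/1,000)] = 0.02997. z = 0.10/0.02997 = 3.34, p = 0.0008.

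Other assumed sizes, with serotype p = 1.00 throughout: 100 against 500 at 10% and 20%, frequency p = 0.018; 400 against 2,000 at 10% and 15%, p = 0.009; 200 against 1,000 at 15% and 20%, p = 0.10.

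**4. Same frequency, different mix.** Carriage is 20% in both groups of 200 and 1,000, with the mix reversed in one. Carriers are 4, 6, 8, 10, 12 against 60, 50, 40, 30, 20. Chi-square = 18.4 on 4 df, p = 0.001. The frequency comparison gives p = 1.00.

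**5. Rejection rates (2,000 simulated studies, 10 equally common serotypes, carriage 10% and 20%, 5% level)**

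| Test | 400 vs 1,600 | 200 vs 800 |
|---|---|---|
| Serotypes, carriers only | about 5% | about 5% |
| Serotypes plus a 'no carriage' row | about 91% | about 40% |
| Carriage proportion | more than 99% | about 95% |

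The carriers-only test stays at its nominal level, so it has no power against a pure difference in frequency. The extra row spreads the single contrast over 10 degrees of freedom and loses power, badly so at the smaller size.

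**The case against.** The strongest reply is that this is a wording conflict within the SAP and that no data are missing for the main question. Both endpoint definitions specify frequency, the heading of SAP 6.3.8 speaks of the frequency distribution of carriage, and saliva results and COVID-19 tests are both planned. This stands against a reading that a reader might infer, namely that the objective cannot be answered at all. The current-infection part can be answered from planned data; only the past-infection part cannot. It does not rescue 6.3.8.1, which remains the operative text and names a different quantity.

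A reader might also infer that untested patients will be counted as free of COVID-19. The documents largely prevent this. SAP 3.3.2 requires a status from testing, SAP 4.8.8 to 4.8.10 require a valid result, and SAP 5.3 excludes participants from analyses for which their data are missing. What remains is a conflict between 6.3.8.1 and these sections.

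The chance-level rejection rate should not be read as the performance of the SAP's test, because 6.3.8.1 does not say that the test is restricted to carriers. With a 'no carriage' row it would detect some frequency differences, though the text states no such row. The simulated inputs are also favourable: at 15% against 20% with 400 and 1,600 patients, even the direct comparison rejects in only about two thirds of studies.

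Finally, the endpoint is exploratory, is analysed only if COVID-19 is frequent enough (Protocol 9.1 and 12.4.3), and carries no decision rule (SAP 5.1). That limits the weight of the point; it is not a reason to leave the text unaligned.

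**Conclusion.** The point holds as an inconsistency that should be corrected. SAP 6.3.8 and 6.3.8.1 analyse the serotype distribution where the objective and both endpoint definitions call for carriage frequency, and no other section makes the frequency comparison by COVID-19 status. The analysis population in 6.3.8.1 also conflicts with SAP 3.3.2. These conclusions rest on the text alone. The numerical illustrations use assumed sizes, rates and serotype mixes and show only that the two tests answer different questions.

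The lack of a data source for past infection is a separate gap. One might infer that placing previously infected patients in the comparator biases the result toward no difference. The documents do not support a direction: it depends on how past infection affects carriage, for which they give no figure.

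The primary vaccine effectiveness analysis and the secondary endpoints are unaffected.

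**What to change.** - **Quantity.** In SAP 6.3.8 and 6.3.8.1, compare the proportion with pneumococcal carriage (culture- or PCR-positive saliva divided by valid saliva results) between participants with a positive and those with a negative valid COVID-19 test in the current illness. Give 95% CIs, overall and by age, sex and risk status. Keep the serotype distribution as a descriptive table.
- **Population.** Build the groups from the subpopulations already in SAP 4.8.9 to 4.8.11. Those are drawn from the per-protocol population, so restrict them to a final diagnosis of CAP (SAP 4.5) to match the endpoint. Remove the reference to cases and controls. SAP 3.4 says that positive and negative COVID-19 results are both documented, so test-negative and untested patients can be told apart.
- **Infection status.** Limit the objective and endpoint wording to current COVID-19 infection, unless the sponsor specifies a source for past infection. The linked primary care records (Protocol 9.1.4) are one candidate, but this would be new collection and the documents do not say how completely those records capture past COVID-19. The choice is the sponsor's.

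**Cost.** Revised SAP text and one revised table, plus an objective reworded at the next amendment. No new patients are needed, and no new data if the objective is limited to current infection. The price of that limit is giving up the past-infection claim.

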# 6.3.9. Additional RSV Related Endpoint 1 – Proportion of CAP events where RSV was identified from Saliva

The proportion of the RSV cases among CAP population will be calculated for which a valid saliva specimen test result for RSV is available.

#### 6.3.9.1. Additional RSV Related Endpoint 1 - Main Analysis

In this analysis the denominator will be CAP population whose a valid saliva specimen test result for RSV is available. Proportion (95% CI for proportion) of RSV infection and other respiratory viruses among the CAP population will be calculated. The proportion will be calculated overall and stratified by age, sex, and pneumococcal risk status.

DMB02-GSOP-RF02 5.0 Statistical Analysis Plan Template 05-Dec-2019
PFIZER CONFIDENTIAL
Page 41
TMF Doc ID: 98.03

#### 6.4. Subset Analyses

Age group, sex, and nationality will be used in the subset analyses. Age at enrolment will be calculated in years as integer ((Date of enrolment/visit - Date of Birth + 1) /365.25). Sex and nationality at enrolment will be used as reported on the CRF. For purposes of analysis, age at enrolment will be broken into the following categories: 60-74 years and 75 years or older.

## 6.5. Baseline and Other Summaries and Analyses

Data will be summarized based on the all enrolled population, showing the number and percent of participants consented, enrolled, completed study and withdrawn from study (including reasons for withdrawal). The number and percent of participants will also be displayed by individual sites within all enrolled, per-protocol, CAP and RAD+CAP associated with Sp+ populations. In addition, the number and percent of participants within each analysis subpopulation will be reported. The following four analyses pertain to information collected at enrollment:

## 6.5.1. Demographic Data

Demographic data will include age, sex, nationality, weight, height, BMI (to be calculated, if not already derived in the data set) and previous enrollment in the study (Yes/No). Weight, height, and BMI will be analyzed as continuous variables, and all others as categorical variables.

# 6.5.2. Risk factors and Significant Medical History

Most of the risk factors are to be analyzed as categorical variables with three categories as present, absent or unknown (recorded as Yes, No and Unknown, respectively on the CRF). Significant medical history will be analyzed as recorded on the CRF (using pre-filled conditions). For each condition, the number and percent of participants in each category, namely, present, absent, unknown and not assessed (recorded as Yes, No, Unknown and Not Assessed, respectively on the CRF) will be displayed. Based on their medical history and risk factors, participants will be grouped into 'at-risk' and 'high-risk' subgroups for analysis. We will analyze per-protocol population breakdown by *Sp*+ versus *Sp*-.

#### 6.5.3. Prior vaccination

Prior vaccination with PCV13 and/ or PPV23 will be summarized as binary (Yes/No) variables (with numbers and percentages). Participants will be divided into ever vaccinated and never vaccinated for each vaccine. The timing of last dose will be presented by year since last vaccination (e.g., <1 year, 1 year, 2 years, etc.) The timing (in years) will be calculated as int((date of visit – date of last dose +1)/365.25). A table with PCV13 exposure in rows and PPV23 exposure in columns will be developed to show the overlap. Proportion with influenza vaccination in the last year will also be displayed. Breakdowns will be provided for final diagnosis of CAP versus final diagnosis of non-CAP.

#### 6.5.4. Culture Data

The number and percentage of cultures performed as well as the number and percentage of pathogens identified will be summarized as frequency distributions for the entire study population.

DMB02-GSOP-RF02 5.0 Statistical Analysis Plan Template 05-Dec-2019
PFIZER CONFIDENTIAL
Page 42
TMF Doc ID: 98.03

Summaries will also be calculated for the specimen source (e.g., blood, pleural fluid, sputum, etc.) as well as for the various organisms within specimen source. Note that a participant may have multiple specimen sources and/or organisms isolated. Organism type (pathogen, for *Sp* only) will also be summarized individually for each culture source as well as combined across all sources. This analysis will be performed for the microbiology culture subpopulation. Breakdowns will be provided for final diagnosis of CAP versus final diagnosis of non-CAP.

## 6.5.5. Viral Testing Data

The number and percentage of viral tests performed as well as the number and percentage of viral pathogens identified will be summarized as frequency distributions for all participants. Note that a participant may have multiple viral pathogens isolated. Pathogen type will also be summarized individually. This analysis will be performed for the viral testing subpopulation within all enrolled population. Breakdown will be provided for final diagnosis of CAP versus final diagnosis of non-CAP. Within CAP and non-CAP, breakdown will also be provided for *Sp*+ versus *Sp*-.

## 6.5.6. Antimicrobial Susceptibility

Antimicrobial susceptibility will be performed on the microbiology culture subpopulation within the CAP population. Only participants with *Sp* isolates (which are confirmed as a pathogen on the CRF) from cultures can contribute to this analysis and participants with responses of 'Not Done' for any antimicrobial test will be excluded. For each *Sp* isolate and a given antimicrobial test, a categorical variable will denote whether the isolate is susceptible, intermediate or resistant as recorded on the CRF. Frequencies and percentages of these three categories will be calculated first for each antimicrobial test overall (across all serotypes) and then for each antimicrobial test grouped further by PCV20, the 7 serotypes in PCV20 but not in PCV13, and non-PCV20 serotypes. Percentages will be calculated out of the total number of *Sp* isolates within each serotype.

The following antimicrobials will be evaluated: penicillin, amoxicillin, cefotaxime, erythromycin, clindamycin, tetracycline, and levofloxacin.

